3.1.5.2 Dose modifications

The following dose modifications will be implemented in case of toxicities:

- Grade 2, 3, or 4 thrombocytopenia:
 - Withhold dosing until resolution to Grade 0 or 1;
 - Resume CAM-H2 at 50% with complete or partial resolution;
 - If a reduced dose does not result in Grade 2, 3, or 4 thrombocytopenia, administer CAM-H2 at the full planned dose for next cycle.
 - Permanently discontinue CAM-H2 for Grade 2 or higher thrombocytopenia requiring a treatment delay of 12 weeks or longer; and
 - Permanently discontinue CAM-H2 for recurrent (defined in this study as occurring after >1 dose of CAM-H2 during Cycle 1) Grade 2, 3, or 4 thrombocytopenia.
- Grade 3 or 4 anemia and neutropenia:
 - Withhold dosing until resolution to Grade 0, 1, or 2;
 - Resume CAM-H2 at 50% in patients with complete or partial resolution;
 - If a reduced dose does not result in Grade 3 or 4 anemia or neutropenia, administer CAM-H2 at full planned dose for next cycle.
 - Permanently discontinue CAM-H2 for Grade 3 or higher anemia or neutropenia requiring a treatment delay of 12 weeks or longer; and
 - Permanently discontinue CAM-H2 for recurrent (defined in this study as occurring after >1 dose of CAM-H2 during Cycle 1) Grade 3 or 4 anemia or neutropenia.
- Renal toxicity (defined as an eGFR <40 mL/minute or a 40% decrease in baseline eGFR):
 - Withhold dosing until resolution to at least 80% of baseline eGFR;
 - Resume CAM-H2 at 50% in patients with complete or partial resolution;
 - If a reduced dose does not result in another decrease of eGFR, administer CAM-H2 at the full, planned dose for next cycle.
 - Permanently discontinue CAM-H2 for eGFR decreases requiring a treatment delay of 12 weeks or longer; and
 - Permanently discontinue CAM-H2 for recurrent (defined in this study as occurring after >1 dose of CAM-H2 during Cycle 1) toxicity.

- Hepatic toxicity (Hy's Law cases):
 - Withhold dosing until resolution to ALT and AST values $<2 \times$ baseline and total bilirubin values of $<1.5 \times$ ULN;
 - Resume CAM-H2 at 50% in patients with complete or partial resolution;
 - If a reduced dose does not result in another transaminase or total bilirubin increase, administer CAM-H2 at full planned dose for next cycle.
 - Permanently discontinue CAM-H2 for transaminase or total bilirubin decreases requiring a treatment delay of 12 weeks or longer; and

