 - Permanently discontinue CAM-H2 for recurrent (defined in this study as occurring after >1 dose of CAM-H2 during Cycle 1) toxicity.
- Hepatic toxicity (patients with hepatic metastases and AST or ALT $>8 \times$ ULN or AST or ALT $>5 \times$ ULN for ≥ 14 days):
 - Withhold dosing until resolution to ALT and AST values of $<1.2 \times$ baseline and total bilirubin values of $<1.5 \times$ ULN;
 - Resume CAM-H2 at 50% in patients with complete or partial resolution;
 - If a reduced dose does not result in another transaminase or total bilirubin increase, administer CAM-H2 at full planned dose for next cycle.
 - Permanently discontinue CAM-H2 for transaminase or total bilirubin decreases requiring a treatment delay of 12 weeks or longer; and
 - Permanently discontinue for recurrent (defined in this study as occurring after >1 dose of CAM-H2 during Cycle 1) toxicity.
- Grade 3 or 4 non-hematological toxicities as listed in the CTCAE version 5.0:
 - Withhold dosing until resolution to Grade 0, 1, or 2;
 - Resume CAM-H2 at 50% in patients with complete or partial resolution;
 - If a reduced dose does not result in Grade 3 or 4 toxicity, administer CAM-H2 at full planned dose for next cycle.
 - Permanently discontinue CAM-H2 for Grade 3 or higher toxicity requiring a treatment delay of 12 weeks or longer; and
 - Permanently discontinue for recurrent (defined in this study as occurring after >1 dose of CAM-H2 during Cycle 1) Grade 3 or 4 toxicities.

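### The 12-week permanent-discontinuation rule in both hepatic dose-modification blocks names the wrong direction of change, and nothing else in the protocol states it correctly

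*Combined protocol and SAP*

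**What the plan says.** Section 3.1.5.2 sets out six toxicity blocks built on one pattern: withhold, resume at half dose, return to full dose if the toxicity does not come back, stop for good after a delay of at least 12 weeks, and stop for good on recurrence.

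In both hepatic blocks the 12-week bullet reads: "Permanently discontinue CAM-H2 for transaminase or total bilirubin decreases requiring a treatment delay of 12 weeks or longer; and". The Dose Modifications part of the synopsis prints the same bullet in both hepatic blocks.

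The other bullets of these blocks run the opposite way. The Hy's Law hold is: "Withhold dosing until resolution to ALT and AST values $<2 \times$ baseline and total bilirubin values of $<1.5 \times$ ULN". The hepatic metastases hold is: "Withhold dosing until resolution to ALT and AST values of $<1.2 \times$ baseline and total bilirubin values of $<1.5 \times$ ULN". The return to full dose in both is: "If a reduced dose does not result in another transaminase or total bilirubin increase, administer CAM-H2 at full planned dose for next cycle". The restart is: "Resume CAM-H2 at 50% in patients with complete or partial resolution".

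Two neighbouring blocks matter for comparison. The renal block has: "Permanently discontinue CAM-H2 for eGFR decreases requiring a treatment delay of 12 weeks or longer; and". The general block for non-hematological toxicity has: "Permanently discontinue CAM-H2 for Grade 3 or higher toxicity requiring a treatment delay of 12 weeks or longer; and", with the hold "Withhold dosing until resolution to Grade 0, 1, or 2".

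**The concern.** A falling ALT, AST or bilirubin is recovery. It starts no hold anywhere in the plan, so a delay caused by such a fall cannot occur, and a rule that depends on one has no literal application.

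This is an operative rule for individual patients, not background text. It decides whether a patient whose liver tests took 12 weeks or more to recover may be given the radioligand again. Section 1.2 describes this as the first human study of this specific construct, and Section 7.4.6 lists the liver as a critical organ for dosimetry. Sites and monitors should not have to infer what a mandatory stop means.

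**Working it through.** No arithmetic applies beyond counting. The check compares the texts and then looks for the rule elsewhere.

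**Step 1. Which direction is toxic?** Section 3.1.4.1 gives the Hy's Law criterion as ALT or AST above 3 × ULN with total bilirubin above 2 × ULN. The metastases block applies to AST or ALT above 8 × ULN, or above 5 × ULN for at least 14 days. Both are elevations.

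**Step 2. Does the 12-week bullet name the toxicity of its block?**

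| Block in Section 3.1.5.2 | Toxicity | Hold ends when | 12-week bullet names | Match |
|---|---|---|---|---|
| Thrombocytopenia | Grade 2 to 4 | Grade 0 or 1 | Grade 2 or higher | yes |
| Anemia, neutropenia | Grade 3 or 4 | Grade 0 to 2 | Grade 3 or higher | yes |
| Renal | eGFR falls | eGFR back to 80% of baseline | eGFR decreases | yes |
| Hepatic, Hy's Law | ALT/AST and bilirubin rise | values fall below ceilings | decreases | **no** |
| Hepatic, metastases | ALT/AST rise | values fall below ceilings | decreases | **no** |
| Other non-hematological | Grade 3 or 4 | Grade 0 to 2 | Grade 3 or higher | yes |

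In every other block this position holds the toxicity itself. *Decreases* is right for eGFR and wrong for liver tests. The wording may have been carried over from the renal block; that is a guess, and nothing depends on it.

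**Step 3. How often is the hepatic rule stated, and how?** Two statements in the synopsis plus two in Section 3.1.5.2 make four. Four say *decreases*; none says *increases*.

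**Step 4. Does other text supply the rule?**
- Section 4.3 (withdrawal) leaves the decision to the investigator and sets no time limit.
- Section 3.1.5.1 (stopping rules) provides for review by the Safety Review Committee and sets no 12-week limit for a patient.
- Section 3.1.5.3 (missed doses) covers production problems and circumstances unrelated to the drug.
- The recurrence bullets cover repeat toxicity, not one slow recovery.
- The cycle-eligibility visits (Sections 6.2.2.9 and 6.3.2.9) call for a safety assessment without a 12-week stop.

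**Step 5. What does the general non-hematological rule cover?** It allows two readings.
- *Broad:* any event that reached Grade 3 and was held for at least 12 weeks, for whatever reason, must stop. A Grade 3 hepatic event kept on hold by the stricter hepatic limits is then covered.
- *Narrow:* only the delay produced by that block's own hold counts, and that hold ends at Grade 2. Further time on the hepatic hold is then not covered.

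On either reading, a hepatic-block event that never reaches Grade 3 is outside the rule. Whether such events exist depends on CTCAE cut-offs, which the documents do not give. Assume that the Grade 3 boundaries are multiples of ULN:
- *Hy's Law block:* if the ALT/AST boundary is at or below 3 × ULN, or the bilirubin boundary at or below 2 × ULN, every event is Grade 3 on entry. If both boundaries are higher, some events fall short.
- *Metastases block:* if the ALT/AST boundary is at or below 5 × ULN, every event is Grade 3 on entry. If it is higher, some may fall short.

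**The case against.** The strongest reply is that this is a copy-editing slip in a rule that still works. The only delay either hepatic block can create is the hold for elevations. The hold limits and the full-dose bullet show the direction, and the parallel bullets all stop treatment at 12 weeks. A site would have to read the bullet literally, conclude that it is empty, and then re-treat. This stands as to intent and as to likelihood. It does not make the text correct.

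The bullet might also be rescued by taking *decreases* to mean a return to the limit that takes 12 weeks or more. That is strained, because the other blocks put the toxicity in that position and the renal block uses the same word for the toxicity itself.

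A further reply is that the general Grade 3 rule is a backstop. That stands in part. A reader might infer that no hepatic event has a valid 12-week stop. The documents do not support this, because the broad reading in Step 5 fits the words of the general rule.

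Other safeguards also limit the consequence. In Cycle 1 both hepatic triggers are dose-limiting toxicities (Section 3.1.4.1). Any such toxicity feeds the committee's recommendation, and two related ones in a cohort stop dosing until resolution (Section 3.1.5.1). None of these is a mandatory 12-week stop.

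**Conclusion.** The point holds as an error of wording in an operative safety rule. All four statements of the hepatic 12-week rule name recovery as the trigger, and no correct statement exists.

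The consequence is low. The clear gap is hepatic-block events that do not reach Grade 3, for example some Hy's Law cases, if the CTCAE boundaries lie above the triggers. For events that did reach Grade 3, the position is ambiguous rather than unprotected. How often a patient would stay on a hepatic hold for 12 weeks cannot be determined from the documents.

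Two stronger inferences should be avoided. One is that patients could be dosed while liver tests are still above the hepatic limits; they could not, because the hold continues until the limits are met. The other is that the bullet would remove patients who are recovering; it would not, because no fall in liver tests starts a delay.

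**What to change.** Replace *decreases* with *increases* in the 12-week bullet of the Hy's Law block and of the hepatic metastases block, both in Section 3.1.5.2 and in the synopsis. All four should change together, since correcting only the body would leave the synopsis in conflict with it. The cost is one word in four places at the next amendment, with no change to procedures, sample size or timelines.

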3.1.5.3 Missed doses

Cycles 1 and 2

During Cycles 1 and 2 (for both the dose escalation and dose expansion phases), if a patient misses Dose 1 of study drug due to study drug production problems (eg, insufficient activity yield, ¹³¹I supply problem), the interval between screening and first dosing (Cycle 1) and/or the interval between the cycle eligibility assessment and first dosing (Cycle 2) may be extended up to an additional 2 weeks to allow for the production of a new batch of study drug. If the patient was eligible per protocol, no screening procedures will be repeated unless deemed necessary following a discussion between the Principal Investigator, Medical Monitor, and Sponsor.

Similarly, if a patient misses Dose 2 of the study drug during Cycles 1 or 2 due to study drug production problems, the interval between Dose 1 and Dose 2 may be extended up to an additional 2 weeks (ie, Dose 2 may occur up to 6 weeks after Dose 1). Safety Follow-Up visits after Dose 2 will be scheduled based on the actual Dose 2 visit date.

Cycles 3 and 4

During Cycles 3 and 4 (for the dose escalation phase), if a patient misses Dose 1 of study drug due to study drug production problems (eg, insufficient activity yield, ¹³¹I supply problem), the interval between the cycle eligibility assessment and first dosing may be extended up to an additional 8 weeks to allow for the production of a new batch of study drug.

Similarly, if a patient misses Dose 2 of the study drug during Cycles 3 or 4 due to study drug production problems, the interval between Dose 1 and Dose 2 may be extended up to an additional 8 weeks (ie, Dose 2 may occur up to 12 weeks after Dose 1). Safety Follow-Up visits after Dose 2 will be scheduled based on the actual Dose 2 visit date.

All cycles

In cases of a missed dose of study drug due to other circumstances unrelated to study drug or procedures (eg, secondary to scheduling conflict, missed appointment), the Investigator should contact the Sponsor or designee to discuss available options in order to make a decision in the patient's best interest. The decision will be documented for the study and site files.

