6.2.2.8 Visit 10 (Week 8)

The following procedures will be performed at Visit 10 (Week 8):

- Assess AEs;
- Perform physical examination;
- Measure vital signs;
- Perform clinical laboratory tests;

Note: Clinical laboratory tests should be performed prior to any imaging.

- Perform urinalysis for kidney biomarkers and for microscopic evaluation of sediment;

- Assess performance status using the ECOG PS; and
- Perform imaging to evaluate disease status.

Note: Diagnostic CT scan will be performed in all patients. Brain MRI will only be performed in patients with known brain metastases.

6.2.2.9 Visit 11 (Week 11): End of Treatment Visit or Cycle 2 eligibility assessment

This visit will also serve as the screening visit for Cycle 2 of the dose escalation phase. Cycle 2 eligibility will be assessed by evaluating disease state and safety. This visit will serve as the EOT Visit for patients who do not have CB.

The following procedures will be performed at Visit 11 (Week 11):

- Update demographics and medical history, including confirmation of lesion size;
- Record prior and concomitant medications, including information on any thyroid-blocking drugs;
- Deliver thyroid-blocking drugs for next visit (only patients eligible for and continuing to Cycle 2);

Note: Patients will not take the thyroid-blocking drugs at this visit but will be instructed to take them 24 hours prior to their next visit (ie, 24 hours prior to study drug administration).

- Perform urine hCG testing in all female patients of childbearing potential (ie, ovulating, premenopausal, and not surgically sterile);
- Collect blood to evaluate serum for ADAs and to measure exploratory biomarkers (from patients who have consented to the procedure);
- Assess AEs;
- Measure weight;
- Perform physical examination;
- Measure vital signs;
- Perform clinical laboratory tests;

Note: Clinical laboratory tests should be performed prior to any imaging.

- Perform triplicate 12-lead ECGs;
- Perform echocardiogram;

Note: LVEF may alternatively be measured using a multigated acquisition scan.

- Perform urinalysis for kidney biomarkers and for microscopic evaluation of sediment; and
- Perform imaging to evaluate disease status (EOT Visit only).

Note: Diagnostic CT scan will be performed in all patients. Brain MRI will only be performed in patients with known brain metastases.

Note: If the patient is continuing to Cycle 2, imaging to evaluate disease status will not be performed.

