6.2.3.2 Visits 12, 21, and 30 (Week 0)

Dose 1 will be administered at Visits 12, 21, and 30 of Cycles 2, 3, and 4, respectively. Week 0 will occur within 2 weeks after the prior eligibility assessment visit. The following procedures will be performed at Visits 12, 21, and 30 (Week 0):

- Admit to radioactive unit for hospitalization prior to study drug administration;

Note: Patients will be admitted during each IV administration for a total of 48 hours. This hospitalization can be shortened if ^{131}I decay and the patient's clearance allow discharge according to the applicable local regulations on radioactive compound exposure.

Note: Before the patient is released, a leaflet containing information on radioprotection rules and general precautions after radiation treatment will be distributed (see [Appendix F](#)).

- Confirm the ingestion of thyroid-blocking drugs at least 24 hours prior to study drug administration;
- Deliver and confirm the ingestion of thyroid-blocking drugs 1 hour prior to study drug administration;
- Deliver and confirm the ingestion of thyroid-blocking drugs 24 and 48 hours after study drug administration;

Note: If the patient is discharged prior to 48 hours, deliver the thyroid-blocking drugs for 48 hours at 24 hours. Patients will still take the thyroid-blocking drugs 48 hours after study drug administration.

- Perform urine hCG testing in all female patients of childbearing potential (ie, ovulating, premenopausal, and not surgically sterile) prior to study drug administration;
- Assess AEs;
- Perform physical examination prior to study drug administration and at 24 hours after study drug administration;
- Measure vital signs prior to study drug administration and 30 minutes, 5 hours, 24 hours, and 48 hours after study drug administration;
- Administer anti-emetic, anti-histamine, and anti-pyretic premedication therapy approximately 30 minutes prior to the start of the amino acid infusion, according to the site's standard operating procedures;
- Administer saline 0.9% infusion, starting 30 minutes prior to study drug administration and continuing for up to 3 hours after, at a rate of 200 to 300 mL/hour;

- Administer an amino acid solution beginning 30 minutes prior to study drug administration and ending 3 hours after study drug administration at a rate of 250 to 500 mL/hour;

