6.2.3.6 Visits 16, 25, and 34 (Week 4)

Dose 2 of Cycles 2, 3, or 4 will be administered at Visits 16, 25, and 34 of Cycles 2, 3, and 4, respectively. The following procedures will be performed at Visits 16, 25, and 34 (Week 4):

- Admit to radioactive unit for hospitalization prior to study drug administration;

Note: Patients will be admitted during each IV administration for a total of 48 hours. This hospitalization can be shortened if ^{131}I decay and the patient's clearance allow discharge according to the applicable local regulations on radioactive compound exposure.

Note: Before the patient is released, a leaflet containing information on radioprotection rules and general precautions after radiation treatment will be distributed (see [Appendix F](#)).

- Confirm the ingestion of thyroid-blocking drugs at least 24 hours prior to study drug administration;
- Deliver and confirm the ingestion of thyroid-blocking drugs 1 hour prior to study drug administration;
- Deliver and confirm the ingestion of thyroid-blocking drugs 24 and 48 hours after study drug administration;

Note: If the patient is discharged prior to 48 hours, deliver the thyroid-blocking drugs for 48 hours at 24 hours. Patients will still take the thyroid-blocking drugs 48 hours after study drug administration.

- Perform urine hCG testing in all female patients of childbearing potential (ie, ovulating, premenopausal, and not surgically sterile) prior to study drug administration;
- Collect blood to evaluate serum for ADAs and to measure exploratory biomarkers (from patients who have consented to the procedure) prior to study drug administration;
- Assess AEs;
- Perform physical examination prior to study drug administration and at 24 hours after study drug administration;
- Measure vital signs prior to study drug administration and 30 minutes, 5 hours, 24 hours, and 48 hours after study drug administration;
- Perform clinical laboratory tests prior to study drug administration;
- Administer anti-emetic, anti-histamine, and anti-pyretic premedication therapy approximately 30 minutes prior to the start of the amino acid infusion, according to the site's standard operating procedures;
- Administer saline 0.9% infusion, starting 30 minutes prior to study drug administration and continuing for up to 3 hours after, at a rate of 200 to 300 mL/hour;

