6.3.3.2 Visit 12 (Week 0)

Dose 1 of Cycle 2 will be administered at Visit 12. Visit 12 will occur at approximately 2 weeks after Visit 11. The following procedures will be performed at Visit 12 (Week 0):

- Admit to radioactive unit for hospitalization prior to study drug administration;

Note: Patients will be admitted during each IV administration for a total of 48 hours. This hospitalization can be shortened if ^{131}I decay and the patient's clearance allow discharge according to the applicable local regulations on radioactive compound exposure.

Note: Before the patient is released, a leaflet containing information on radioprotection rules and general precautions after radiation treatment will be distributed (see [Appendix F](#)).

- Confirm the ingestion of thyroid-blocking drugs at least 24 hours prior to study drug administration;
- Deliver and confirm the ingestion of thyroid-blocking drugs 1 hour prior to study drug administration;
- Deliver and confirm the ingestion of thyroid-blocking drugs 24 and 48 hours after study drug administration;

Note: If the patient is discharged prior to 48 hours, deliver the thyroid-blocking drugs for 48 hours at 24 hours. Patients will still take the thyroid-blocking drugs 48 hours after study drug administration.

- Perform urine hCG testing in all female patients of childbearing potential (ie, ovulating, premenopausal, and not surgically sterile) prior to study drug administration;
- Assess AEs;
- Perform physical examination prior to study drug administration and at 24 hours after study drug administration;
- Measure vital signs prior to study drug administration and 30 minutes, 5 hours, 24 hours, and 48 hours after study drug administration;
- Administer anti-emetic, anti-histamine, and anti-pyretic premedication therapy approximately 30 minutes prior to the start of the amino acid infusion, according to the site's standard operating procedures;
- Administer saline 0.9% infusion, starting 30 minutes prior to study drug administration and continuing for up to 3 hours after, at a rate of 200 to 300 mL/hour;
- Administer an amino acid solution beginning 30 minutes prior to study drug administration and ending 3 hours after study drug administration at a rate of 250 to 500 mL/hour;

- Administer study drug via slow IV infusion, ie, administer using a shielded infusion device over approximately 3 to 30 minutes, depending on the volume to be injected; and

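### When a production problem postpones Dose 1 of a later cycle, the last required hematology and chemistry can be about 28 days old (Cycle 2) or 70 days old (escalation Cycles 3 and 4), and no repeat is required before infusion

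*Combined protocol and SAP*

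**What the plan says.** **Entry to a later cycle.** Sections 3.1.1.2 and 3.1.2.2 allow the next cycle once the Week 11 safety assessments are done and reviewed. Those assessments include clinical laboratory tests (Visit 11 in Sections 6.2.2.9 and 6.3.2.9; Visits 20 and 29 in Section 6.2.3.10). Of Visit 11 in escalation, Section 6.2.2.9 says: "This visit will also serve as the screening visit for Cycle 2 of the dose escalation phase". In expansion the same visit is called an eligibility assessment.

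**Planned timing of Dose 1.** Escalation: "Week 0 will occur within 2 weeks after the prior eligibility assessment visit" (Section 6.2.3.2). Expansion: "Visit 12 will occur at approximately 2 weeks after Visit 11" (Section 6.3.3.2).

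**Delay after a production problem (Section 3.1.5.3).** For Cycle 2 in both phases, "the interval between the cycle eligibility assessment and first dosing (Cycle 2) may be extended up to an additional 2 weeks". For escalation Cycles 3 and 4, "the interval between the cycle eligibility assessment and first dosing may be extended up to an additional 8 weeks".

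**Repeat testing.** The paragraph on Cycles 1 and 2 says that for an eligible patient "no screening procedures will be repeated unless deemed necessary" after discussion between the Principal Investigator, Medical Monitor and Sponsor. The paragraph on Cycles 3 and 4, which allows the longer delay, does not mention repeat testing.

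**Checks at the dosing visits.** The Dose 1 lists (Visits 12, 21 and 30 in Section 6.2.3.2; Visit 12 in Section 6.3.3.2) require urine hCG in women of childbearing potential, physical examination and vital signs before infusion, plus adverse event assessment. Neither list contains hematology or chemistry. The Dose 2 list in Section 6.2.3.6 does: "Perform clinical laboratory tests prior to study drug administration". Section 6.3.3.6 has the same requirement for expansion.

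**The concern.** The hematologic, renal and hepatic holds in Section 3.1.5.2 can only work on current laboratory values. A patient with acceptable values at Week 11 who later crosses a threshold without symptoms could receive a postponed Dose 1 with no deviation from the plan.

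These patients have already been exposed to CAM-H2. Section 1.3.2 predicts that the kidneys will be the dose-limiting organ, and Section 8.1.4 names renal failure and myelodysplastic syndrome as events of special interest. Table 1 schedules no SPECT/CT after Cycle 1, and the 23 Gy kidney limit relies on Cycle 1 dosimetry. In later cycles, blood chemistry is therefore the most direct look at kidney function.

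The plan treats the two doses of a cycle differently. A Dose 2 given as late as the section allows still has its own pre-dose panel. A Dose 1 postponed for the same reason does not.

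**Working it through.** **1. How the plan counts the extra weeks.** Section 3.1.5.3 gives totals only for the interval from Dose 1 to Dose 2, which is nominally 4 weeks.
- Cycles 1 and 2: 4 + 2 = 6 weeks, as stated.
- Cycles 3 and 4: 4 + 8 = 12 weeks, as stated ("Dose 2 may occur up to 12 weeks after Dose 1").

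So the extension is added to the nominal interval.

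**2. The same rule applied from eligibility visit to Dose 1** (nominal 2 weeks = 14 days, from Sections 6.2.3.2 and 6.3.3.2).

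| Case | Age of last required panel | With the +3-day Dose 1 window |
|---|---|---|
| No delay | 14 days | 17 days |
| Cycle 2, full delay | 14 + 14 = 28 days | 31 days |
| Escalation Cycles 3 and 4, full delay | 14 + 56 = 70 days | 73 days |

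The full delay doubles the planned interval in Cycle 2 (28/14 = 2) and multiplies it by five in Cycles 3 and 4 (70/14 = 5).

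**3. Time since the previous infusion.** The Week 11 visit is Day 50 counted from Dose 2, which is 49 days after it. Cycle 2: 49 + 28 = 77 days (11 weeks). Cycles 3 and 4: 49 + 70 = 119 days (17 weeks).

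**4. Could another scheduled panel fall in the gap?** Table 1 has disease CT every 8 weeks after Week 8, so the next would be at Week 16, 5 weeks after Week 11. A fully delayed Dose 1 falls 10 weeks after Week 11, so that CT is 10 − 5 = 5 weeks = 35 days earlier. Table 8 has a footnote that laboratory tests should precede imaging. If that is read as attaching a panel to this CT, the age in Cycles 3 and 4 falls from 70 to 35 days. The footnote sets an order; it does not clearly require a panel.

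**5. Check against the schedule tables.** Table 10 (expansion Cycle 2) shows 1 + 4 + 4 = 9 laboratory marks. The visit lists name nine occasions: Visit 11; Visits 13, 14, 15 and 16 (pre-dose); Visits 17, 18, 19 and 20. That leaves none for Visit 12. The table's columns are broken in the text, so this is support rather than proof. Table 8 (escalation Cycles 2 to 4) has lost its safety-assessment rows, so the same count cannot be made there.

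**6. Who can reach the 70-day case.** At the projected 34.9 mGy/mCi (Section 1.3.2), kidney dose per cycle is 3.49, 6.98, 10.47 and 13.96 Gy at Levels 1 to 4 (100, 200, 300 and 400 mCi). Compare cumulative dose with the 23 Gy limit:
- If the limit must cover the coming cycle, Cycle 3 is open to Levels 1 and 2 (10.47 and 20.94 Gy; Level 3 is 31.41). Cycle 4 is open to Level 1 only (13.96 Gy; Level 2 is 27.92).
- If it counts only cycles already given, Cycle 3 is open to Levels 1 to 3 (up to 20.94 Gy; Level 4 is 27.92) and Cycle 4 to Levels 1 and 2 (up to 20.94 Gy; Level 3 is 31.41).

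Measured dosimetry may differ from the projection.

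**7. Margin to the renal hold.** Entry requires eGFR above 59 mL/minute (Section 4.1), and the hold applies below 40 mL/minute or at a 40% fall (Section 3.1.5.2). From 60, the first criterion is met after a fall of just over 60 − 40 = 20 mL/minute (33%). This comes before the 40% criterion (0.4 × 60 = 24 mL/minute).

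**The case against.** **The patient is not infused unchecked.** A reader might infer that a postponed Dose 1 goes ahead with no pre-dose assessment. The documents say otherwise: pregnancy testing where applicable, physical examination with full neurologic examination, vital signs and adverse event assessment are all listed, and the Medical Monitor reviews safety data continuously (Section 3.1.5.1). This stands. The gap is limited to hematology and chemistry, and ongoing review cannot act on a result that was never drawn.

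**The plan routinely doses on an earlier panel.** Cycle 1 Dose 1 also has no pre-dose panel, so a reader might infer that the usual 2-week gap is itself a defect. It is not: without delay, the Week 11 panel follows panels at Weeks 5, 6 and 8 and has been reviewed. Only the unguarded extension is at issue.

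**The Cycle 2 case is modest.** The age is 28 days and a repeat is allowed by discussion. Because expansion calls Visit 11 an eligibility assessment and not a screening visit, it is not certain that the no-repeat default reaches it. This stands and makes Cycle 2 secondary. Even so, nothing requires a repeat.

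**The 70-day case may affect nobody.** It needs a full 8-week production delay and clinical benefit through at least two cycles in a phase of at most 18 patients. This stands.

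**Harm is not demonstrated.** The delay is time off drug, Section 3.1.4 expects kidney activity to decline rapidly after infusion, and the documents give no rate at which acceptable values deteriorate. The kidney-dose figures show who can reach a cycle and do not measure that rate. A toxicity already known at Week 11 would in practice need a new test to show resolution.

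**Table 8 might list the test.** Section 8.7 defers to Appendix A for timing, so a reader should not infer that the full schedule omits the panel at Visits 12, 21 and 30. This limits confidence for escalation.

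**Conclusion.** The concern holds for postponed Dose 1 visits. The last required hematology and chemistry can be up to about 70 days old in escalation Cycles 3 and 4 and about 28 days old in Cycle 2 of either phase, with visit windows ignored, and no repeat is required before infusion. The Cycles 3 and 4 case matters most because the delay is longest and the text says nothing on repeats.

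The day counts assume the full extension is used, that it is added to the 2-week interval as the plan does for Dose 2, and that no panel is tied to an intervening CT. Confidence is medium for escalation, where the finding rests on the visit list in Section 6.2.3.2. For expansion, the visit list in Section 6.3.3.2 and the mark count in Table 10 agree.

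The documents do not show that patients would be harmed, or that the long delay would be common. The case for change is that the Section 3.1.5.2 holds could be applied to stale values in previously exposed patients, and that the safeguard the plan already uses at Dose 2 is inexpensive.

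**What to change.** Add to Section 3.1.5.3 and the matching synopsis text:

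> If Dose 1 of Cycle 2, 3 or 4 is postponed under this section so that it falls more than 17 days after the eligibility visit (2 weeks plus the 3-day visit window), repeat local hematology and chemistry (platelets, neutrophils, hemoglobin, creatinine/eGFR, ALT, AST, total bilirubin) within 7 days before infusion and review the results against Section 3.1.5.2 before dosing.

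In the Cycles 1 and 2 paragraph, put the words *Except for these repeat laboratory tests* before "no screening procedures will be repeated unless deemed necessary", so that the section does not contradict itself.

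The 17-day trigger (14 + 3) spares patients dosed on schedule within the visit window. Under this rule the panel is at most 7 days old at a Dose 1 that triggers it, and at most 17 days old otherwise. Check Table 8 at the same time; if it already requires a panel at Visits 12, 21 and 30, bring Section 6.2.3.2 into line with it.

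The cost is one local blood draw per postponed Dose 1. All the listed tests are local analytes in Appendix B. A late hold could waste a batch, given the 144-hour (6-day) shelf life, but a draw up to 7 days ahead can be read before the replacement batch is made or shipped. A routine pre-dose draw at every Visit 12, 21 and 30 is optional and not needed for this fix. No threshold, DLT definition or Cycle 1 procedure changes.
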